## Sensitivity analyses

The primary and secondary analyses will be repeated:

- a. Excluding outliers
- b. In the per protocol population, defined as: Participants needed to attend a minimum of eight physical meetings, incorporating elements from the initial sessions (the family-centered lifeline, resilience and vulnerability mapping, and family-centered psychoeducation about emotions or diagnosis). Additionally, adhering to the intervention protocol required participants to engage in at least two other intervention components from the VIA Family intervention.
- c. Without adjustment for baseline covariates
- d. In case of differential drop out: with further adjustment for potential post randomization confounders.

Results from the sensitivity analyses will only be reported if they differ from the main analyses.

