### Statistical Analyses

All analyses will be performed in the intention-to-treat (ITT) population including study participants as randomized regardless of treatment adherence and dropout status. The analyses will be conducted using the statistical software R^11 after the last participant completes the follow-up assessment and after the formulation of the statistical analysis plan. A two-tailed p-value of < 5% will be considered statistically significant.

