Parental Stress (higher score more stress)	PSS, mean (SD)					
Family functioning (lower score better functioning)	FAD, mean (SD)					
Employment status parents						
Currently employed or studying 	Interview , n (%)					
Educational level parents						
Primary/lower secondary	n (%)					
Upper secondary, vocational, or short-cycle tertiary	n (%)					
Bachelor's degree, equivalent, or higher	n (%)					
Support at baseline (family)	n					
Family receiving support from municipalities/MHS six months prior to baseline 	Interview / Data from municipalities, n (%)					

1 Current Diagnosis within the last 8 weeks, excl. Elimination Disorder, Simple Phobia, Tics/Tourette's Syndrome  
 2 For children living 50/50 with mother and father, the HOME interview was done in both homes  
 3 Child has only one caregiver  
 4 During child's life (including the prenatal period)  
 5 Personality disorder, substance abuse, ADHD, PTSD, or eating disorder  
 6 Any form of employment, no minimum working hours, absence from work due to e.g., illness or maternity leave included as work  
 ADHD-RS Attention Deficit Hyperactivity Disorder Rating Scale; BRIEF Behavior Rating Inventory of Executive Function; CALS Children's Affective Liability Scale; CBCL Child Behavior Checklist; CGAS Children's Global Assessment Scale; CTS Childhood Trauma Screener; FAD Family Assessment Device, HOME Home Observation for Measurement of the Environment; K-SADS-PL Kiddie Schedule for Affective Disorders and Schizophrenia - Present and Lifetime; PSP Personal and Social performance Scale; PSS Parental Stress Scale; RCFT Rey Complex Figure Test; RIST Reynolds Intellectual Screening Test; SCAN Schedules for Clinical Assessment in Neuropsychiatry; SRS-2 Social Responsiveness Scale- Version 2; TOMAL-II Test of Memory and Learning, 2nd Edition; WISC-IV Wechsler Intelligence Scale for Children, 4th Edition

**Primary and secondary analyses** Changes in child-specific outcomes (CGAS, SDQ, KIDSSCREEN, TIM, HOME, PS) will be analyzed using a linear mixed model including allocation group, baseline measurement, child age,

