and sex (registered at birth) as fixed effects and a random effect of family to address non-independence among siblings within the same family.

Changes in parent- and family-specific outcomes (FAD, PSP, PSS) including allocation group, baseline measurement, and parental diagnosis as covariates.

Mean differences in change between the VIA Family intervention and TAU groups, along with a 95% confidence interval, will be reported with corresponding p-values.

Model assumptions will be assessed using residual diagnostics. Severely skewed outcomes will be log-transformed prior to analysis.

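### The per-protocol analysis restricts the VIA Family arm by attendance and gives no rule for TAU, so its contrast is open to confounding by engagement in an unknown direction

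*SAP*

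**What the plan says.** The main analyses are by intention to treat: "All analyses will be performed in the intention-to-treat (ITT) population including study participants as randomized regardless of treatment adherence and dropout status". The quantity reported is a two-arm contrast: "Mean differences in change between the VIA Family intervention and TAU groups, along with a 95% confidence interval, will be reported".

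The Sensitivity analyses section then states that "The primary and secondary analyses will be repeated" under four variations. Item b is the per-protocol population. It has two entry criteria:

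- "Participants needed to attend a minimum of eight physical meetings, incorporating elements from the initial sessions" (the lifeline, the mapping exercise and the psychoeducation);
- "adhering to the intervention protocol required participants to engage in at least two other intervention components from the VIA Family intervention".

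Both describe receipt of VIA Family content. No section of the SAP says which TAU families belong to this population. The section closes by limiting publication of sensitivity results to those that depart from the main results.

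Child outcomes use a "linear mixed model including allocation group, baseline measurement, child age" and sex, with a random family effect. The models for FAD, PSP and PSS use baseline measurement and parental diagnosis.

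**The concern.** A VIA-minus-TAU difference needs a defined set of families in each arm, and item b defines one only. The workable reading keeps every TAU family and drops the VIA families that fell short of the threshold. Adherence is observed after randomisation, and only VIA families can be sorted by it. The TAU arm still contains the families that would not have adhered had they been offered VIA, while the VIA arm no longer does. If such families have a different four-year course for reasons unrelated to the intervention, the contrast shifts even when VIA has no effect.

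What is at stake is the interpretation of a secondary result. A per-protocol estimate that departs from the intention-to-treat estimate could be taken as information about the effect of VIA when received, when it may reflect who attends. Under the closing rule of the section, a departure produced by selection would be published, and agreement would not.

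**Working it through.** **Check of the text.** The SAP contains no per-protocol figure, sample size, SD or attendance rate, so there is no number of the plan's own to reproduce. Setting the parts side by side:

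- Contrast needed: VIA minus TAU (Primary and secondary analyses).
- Families defined by item b: those who received a stated amount of VIA.
- Rule for TAU: none.
- Adjustment for engagement: only what baseline score, age and sex, or baseline score and parental diagnosis, happen to carry. Primary motivation for joining is used to form a subgroup (Subgroup analyses, item e) but is not a model covariate.
- Method that accounts for adherence while preserving randomisation: none.

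**Illustration of size.** The assumptions, none of them from the SAP, are:

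- the true effect is zero;
- a share p of VIA families meets item b;
- a family adheres when a standardised latent engagement score U exceeds a cut-off q, with Φ(q) = 1 − p;
- after covariates, U has correlation ρ with the four-year outcome, coded so that positive ρ means engaged families do better.

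Among adherers the mean of U is φ(q)/p. Among all TAU families it is 0. Hence

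bias (in residual SD) = ρ × φ(q)/p.

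- p = 0.6: q = −0.253, φ(q) = 0.386, ratio 0.386/0.6 = 0.644.
- p = 0.8: q = −0.842, φ(q) = 0.280, ratio 0.280/0.8 = 0.350.

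| p | φ(q)/p | \|ρ\| = 0.1 | \|ρ\| = 0.2 | \|ρ\| = 0.3 |
|---|---|---|---|---|
| 0.6 | 0.644 | 0.064 | 0.129 | 0.193 |
| 0.7 | 0.497 | 0.050 | 0.099 | 0.149 |
| 0.8 | 0.350 | 0.035 | 0.070 | 0.105 |

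The sign is that of ρ. The bias is zero if ρ = 0 or if every VIA family adheres.

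A simulation under the null, with p of 0.6 and 0.8 and ρ of 0.1 and 0.3, gave adherers-versus-all-TAU differences of 0.034 to 0.195 SD. The intention-to-treat differences in the same runs were −0.002 to 0.003 SD.

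**Conversion to points.** Because ρ is defined after covariates, the multiplier must be the residual SD. An assumed residual SD of 6 SDQ points gives 0.350 × 0.1 × 6 = 0.21 to 0.644 × 0.3 × 6 = 1.16 points. If 6 is instead the total SD and the covariates correlate 0.6 with the outcome, the residual SD is 6 × √(1 − 0.36) = 4.8 and the range is 0.17 to 0.93 points.

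**What the alternative does.** With adherence set to 0 in TAU, the unadjusted complier-average effect is the intention-to-treat difference divided by p. Under a true null it is therefore centred near zero whatever ρ is. Its interval is wider by roughly 1/p: 1/0.8 = 1.25 or 1/0.6 = 1.67, ignoring sampling error in p.

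**The case against.** **A reader might infer that the control arm is empty.** Taken word for word, no TAU family meets item b, and the comparison could not be made. That reading is too literal. The second criterion speaks of adherence to the intervention, and the analyses being repeated are two-arm differences, so VIA adherers against all TAU is the evident intent. The omission needs a clarifying sentence.

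**A reader might infer that the bias favours VIA.** Poor attendance could go with family instability and worse outcome. The SAP does not say so, and the reverse is also plausible. Subgroup item e distinguishes families who joined to obtain support, and needier families may attend more, which would bias item b against VIA. Only openness to bias can be asserted.

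**The point applies to per-protocol analyses in general, and this is only a sensitivity analysis.** That is true, and nothing in the SAP says item b will override the intention-to-treat result. The point still stands here because the SAP writes its own definition, covers one arm with it, and plans no method or label that deals with the selection. The selective reporting rule covers all four sensitivity analyses and results in either direction, so it is not a fault of item b in particular.

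**An instrumental estimate largely rescales the intention-to-treat result.** This also stands: it adds little independent evidence of efficacy. Its merit is that it addresses the effect in adherers without discarding randomised families.

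**Conclusion.** The point holds as a weakness of one sensitivity analysis. Item b fixes adherence for VIA only, and its workable reading gives a contrast that randomisation no longer protects. The planned covariates remove only the part of the engagement difference that they explain. On the stated assumptions (60% to 80% adherence, |ρ| 0.1 to 0.3, normal latent engagement, no true effect) the remaining bias is about 0.035 to 0.19 residual SD, in either direction, and nil if engagement is unrelated to outcome. These figures show scale and are not estimates for this trial, because the SAP supplies neither adherence nor ρ nor an SD. The intention-to-treat primary analysis is untouched. The change should be made, but the main conclusion does not depend on it.

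**What to change.** 1. Replace or accompany item b with a complier-average causal effect. Use allocation as the instrument for a yes/no indicator of meeting item b's existing adherence definition, set to 0 for all TAU families. Keep every randomised family, the same covariates as the main model, and allowance for clustering within family.
2. Add the adherence indicator to the imputation model for the VIA arm. Table 2 does not list attendance, and imputation is already run separately by arm.
3. Report this estimate whether or not it differs from the main analysis.
4. If the adherers-versus-TAU comparison is kept, state that all TAU families are retained, and label it a non-randomised comparison that does not count as support for the main result.

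The cost is a few sentences in the SAP and one further model per outcome, using attendance data that item b already requires. The statistical price is the wider interval and the assumption that allocation has no effect on families below the threshold, including those who attended some meetings. A version scaled per meeting avoids the threshold, but it drops item b's content criteria and assumes a linear effect of each meeting. It also assumes that TAU families received no VIA components, which the two-arm design implies but the SAP should state.

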## Hypotheses

We expect that the experimental intervention VIA Family has positively impacted long term improvements in parenting, home environment, parent- and family functioning and other parental and family-related factors of protection for their children. We therefore expect that we will observe greater improvements in child functioning (CGAS), less signs of mental health (SDQ), improved child quality of life (KIDSCREEN) and improved self-esteem (TIM) at 4-years follow-up, along improvements in parent and family related outcomes (PS, PSS, HOME, FAD, PSP) in families allocated to VIA Family compared with TAU.

The primary hypothesis is:

- The VIA Family intervention will demonstrate a superior change in SDQ from baseline (timepoint 0) to 4-year follow-up (timepoint 2) compared with TAU.

The secondary hypotheses are:

- The VIA Family intervention will demonstrate superior change in CGAS, KIDSSCREEN, TIM, HOME, FAD, PSS, PS, and PSP, respectively from baseline (timepoint 0) to 4-year follow-up (timepoint 2) compared with TAU.

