### Handling of missing data

Characteristics of dropouts and completers will be compared between the allocation groups in descriptive tables to identify any possible systematic patterns or reasons for participant discontinuation. Reasons for dropout will be reported.

Missing data in the primary and secondary analyses will be handled by standard multiple imputations using the mice-package and Amelia-package in R. Missing values in each treatment arm separately will be imputed 100-fold including the variables specified in Table 2 below. Convergence will be assessed by traceplots.

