## Subgroup analyses

To explore whether the intervention's effects vary among different demographic or clinical subgroups, the primary analysis will be repeated within the following subgroups:

- a. Children without neurodevelopmental disorders (ASD, ADHD) compared with children with neurodevelopmental disorders at baseline and at end-of-intervention (1.5 years follow-up).
- b. Families with young children, i.e., 6-9 years at baseline compared with families with older children, i.e., 10-12 years at baseline.
- c. Families with low functioning at baseline (characterized by the 35% lowest combined scores in CGAS, HOME and PSP).
- d. Families where all family members (parents and all children) have been participating in at least the introductory sessions of VIA Family compared with families where not all family members participated.
- e. Families whose primary motivation to participate at baseline was to receive support compared with families whose primary motivation was to support a scientific project.

Estimated treatment differences from the subgroups will be reported in forest plots.

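### Sensitivity results go unreported unless judged to differ, by no stated criterion; item d, on its most natural reading, may also stop estimating the as-randomised effect

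*SAP*

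**What the plan says.** The Sensitivity analyses section repeats the primary and secondary analyses in four ways: a, without outliers; b, in a per-protocol population; c, "Without adjustment for baseline covariates"; and d, "In case of differential drop out: with further adjustment for potential post randomization confounders". It ends with the reporting rule: "Results from the sensitivity analyses will only be reported if they differ from the main analyses".

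Four other places bear on this.

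- **Statistical Analyses:** "All analyses will be performed in the intention-to-treat (ITT) population including study participants as randomized regardless of treatment adherence and dropout status".
- **Primary and secondary analyses:** the child outcomes use a "linear mixed model including allocation group, baseline measurement, child age" and sex, with a random family effect. All covariates are measured at baseline.
- **Hypotheses:** the expectation is that "VIA Family has positively impacted long term improvements in parenting, home environment, parent- and family functioning and other parental and family-related factors of protection".
- **Subgroup analyses:** "Estimated treatment differences from the subgroups will be reported in forest plots", with no condition attached.

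On dropout, Handling of missing data says "Characteristics of dropouts and completers will be compared between the allocation groups in descriptive tables" and sets no threshold. The same section imputes missing values separately by arm with the variables of Table 2. For SDQ these include the 18-month value.

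**The concern.** **Reporting rule.** A sensitivity analysis is there to show the reader how far a result depends on a choice. Under this rule agreement is never shown, and no section says whether a difference is judged on the p-value, the estimate or the interval, or how large it must be. A missing result could mean that the analyses agreed closely, that they were judged close enough, or, for item d, that the analysis was never run. The reader cannot tell which.

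**Item d.** A variable measured after randomisation cannot confound the randomised comparison. If the intervention changes that variable, putting it in the outcome model removes part of the effect the trial set out to estimate. Item d names no variables, time point or method, and does not say what makes dropout differential, so nothing keeps affected variables out.

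The two points compound. An item d result that departs from the main result only because it estimates a different quantity is one that the rule would publish, while reassuring results stay unseen.

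**Working it through.** The SAP gives no sample size, effect size, SD or dropout rate, so there is no figure to reproduce. All numerical inputs below are assumed. They show direction and sensitivity, not the size to expect in this trial.

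**1. How many results the rule covers.** There is one primary outcome (SDQ) and eight secondary outcomes (CGAS, KIDSCREEN, TIM, HOME, FAD, PSS, PS, PSP), so nine in all. With four items, 9 x 4 = 36. This is a ceiling: without item d it is 9 x 3 = 27.

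**2. How far the unstated criterion matters, using item c on one outcome.** Assumed: 40, 60 or 80 children per arm; true effect -0.2 or -0.4 SD; correlation of baseline with follow-up 0.5 or 0.6; complete data; no sibling clustering. That makes 12 settings. Item c and the main model target the same effect here, so any difference is chance. Item c does not say whether the baseline score counts among the covariates removed, so both readings matter. The second reading also assumes a correlation of 0.15 with the outcome for age and for sex.

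| Meaning of a difference | Item c drops the baseline score | Item c drops only age and sex |
|---|---|---|
| p crosses 0.05 | about 11-27% of trials | about 5-10% |
| estimate moves by more than 0.1 SD | 20-46% | 1-8% |
| estimate moves by more than 20% | 33-73% | not quoted |
| estimate falls outside the main 95% CI | 0.2-1.6% | not quoted |

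On the first reading alone, the chance that a result is published runs from under 2% to over 70%, depending on a criterion the SAP leaves open.

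**3. What item d estimates if it adds a post-randomisation covariate.** Let A be the arm, B baseline SDQ, M an 18-month variable with variance 1 within arm and correlation 0.5 with B, and U an unmeasured common cause of M and the outcome Y. U has coefficient q on M and g on Y, and correlation s with B. The effect of A on M is a, of M on Y is b, and the direct effect of A on Y is c. The as-randomised effect is c + ab, fixed at -0.20 SD. Regressing Y on A, B and M gives for A:

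c - a x g x q x (1 - s^2) / (1 - 0.25)

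- a = 0 (the intervention does not affect M): c = -0.20, so the result is -0.20. No harm.
- a = -0.4, no common cause: with 25% mediated, c = -0.15; with 50%, c = -0.10. The results equal c.
- a = -0.4, q = g = 0.3, s = 0: the added term is 0.4 x 0.09 / 0.75 = 0.048, giving -0.102 and -0.052.
- The same with s = 0.7: the added term is 0.048 x 0.51 = 0.024, giving -0.126 and -0.076.

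Simulation with dropout that differs by arm agrees (-0.149 and -0.100; -0.100 and -0.050; -0.124 and -0.076).

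**4. The same variable used only for imputation.** In the same simulation, by-arm imputation from B and M with the outcome model unchanged gives -0.196 to -0.201 when data are missing at random. A separate simulation with a true effect of 0.30 gives 0.298 to 0.304. Protection is not complete: if leaving before 18 months depends on the unobserved 18-month value, the main analysis gives -0.169 to -0.192.

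**The case against.** **Item d may mean something harmless.** Table 1 sets out baseline characteristics by arm and dropout status. A reader coming from it could take item d to mean baseline characteristics that become unbalanced through selective loss. Adjusting for those would not change the target. This reading remains open. Against it, item c in the same list uses adjustment for covariates in the model and calls those baseline, while item d calls its own post-randomisation.

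**The harm is conditional.** It needs both the covariate reading and a variable that the intervention affects. The Hypotheses section states expectations about parenting, home and family factors; it is not a list of item d covariates. The biased figures assume an effect of -0.4 on M, twice the total effect on the outcome. When the intervention does not affect M and early leaving depends on M, item d (-0.196 to -0.202) does better than the main imputation (-0.169 to -0.192). All of this stands, so the bias figures show direction only.

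**The reporting rule discloses disagreement.** A reader might infer that the rule is designed to hide unfavourable checks. The text does not support that: as written it publishes discrepancies and omits agreement, and no section suggests a biased judgement. Nor do the unconditional forest plots for subgroups contradict it; they only show that unconditional reporting is feasible. What remains is that the judgement is post hoc and without a criterion.

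**The percentages are fragile.** They depend on what item c drops, and they ignore clustering and missing data. This is accepted, and both readings of item c are shown.

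**Conclusion.** The reporting rule is the main point and needs no interpretation. Followed as written, it withholds every sensitivity result judged afterwards not to differ, by a criterion nobody has stated. The size of the problem cannot be fixed from the SAP. On assumed inputs, the share of trials in which item c would be published varies many-fold with the criterion and with what item c removes.

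Item d is a secondary, conditional point. On its most natural reading, and if the intervention affects the added variables, it estimates something other than the as-randomised effect and carries no label saying so, unlike the per-protocol analysis in item b. A reader might infer that item d must condition on mediators, or that the primary result is biased. The SAP supports neither: item d's wording is open, and the main model uses baseline covariates only. The SAP should be amended on both points, but neither threatens the primary analysis.

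**What to change.** **Reporting.** Delete the closing sentence of the Sensitivity analyses section. Report all sensitivity estimates with 95% CIs in a supplement, and state whether item d was triggered. Say what counts as differential dropout, and which covariates item c removes.

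**Item d.** Keep the outcome model to baseline covariates; adding baseline characteristics that differ by dropout status is acceptable. Name the post-randomisation predictors of dropout in advance, and use them only in the imputation model or in retention weights. If a model with post-randomisation covariates is still wanted, label it as estimating a different quantity.

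For SDQ, the main imputation already uses 18-month data, so moving item d into the imputation would largely repeat the main analysis. An informative check there needs retention weights, additional predictors, or a delta-adjusted imputation by arm over a stated range. For FAD and PS, it needs rows that Table 2 lacks.

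**Cost.** Revised wording, a little more analysis work (a re-run of the imputation or a set of weights), and one supplementary table.
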